8. *Objectives*

The objective of this research study is to better understand patterns of recovery after total hip arthroplasty (THA) and total knee arthroplasty (TKA). The study will evaluate how pain, pupil diameter as a measure of LC activity and cognitive (i.e., thinking style) determine patterns of recovery, and the study will evaluate the efficacy of gabapentin versus placebo for improving recovery after surgery.

Research hypothesis: The null hypothesis (H_0) is that modeled trajectory of change in pain intensity report after THA and TKA does not differ between oral gabapentin and placebo in a manner dependent on its interaction with preferred cognitive style and pre-surgery pupil resting diameter. The alternative hypothesis (H_1) is that there is a difference between the two groups which is dependent on these interactions. The null hypothesis will be tested through contrasting the fit of a null model (m_0), with only change parameters and prognostic covariates, and the full model (m_1), which includes all of the predictors in null model with the addition of randomized treatment group, cognitive style, resting pupil diameter, and all two and three-way interactions. The difference in fit will be evaluated using a likelihood ratio test, as further described below.

$$H_0: -2 * (\loglik[m_0] - \loglik[m_1]) = 0$$

$$H_1: -2 * (\loglik[m_0] - \loglik[m_1]) > 0$$

Study objective: The primary objective is to determine the effectiveness of oral gabapentin to speed recovery from pain, as measured by growth curve modeling, after THA or TKA and how this effectiveness is modified by preferred cognitive style and pre-surgery resting pupil diameter.

Secondary objectives are planned to explore the role of these factors interact to predict other outcomes from surgery, including speed of gain in activity, assessed by actigraphy, speed recovery from self-assessed disability, and time to cessation of opioid use; to explore whether change in pupil diameter to acute experimental pain explains additional variance in a 4-way interaction compared to the 3-way interaction in the primary analysis.

Section 3: Trial Methods

9. Trial design

[figure not shown]
The trial is a two-center, randomized, double-blinded, parallel-group, placebo-controlled trial. Treatment allocation is a 1:1 ratio. Patients are randomized to either gabapentin or placebo control.

10. Randomization

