A computer-generated randomization using a 1:1 allocation ratio in permuted blocks of 8 will be developed by the study statistician uninvolved with data collection and administered by the research pharmacist at Wake Forest School of Medicine. The 'blockrand' package in R will be used by the study statistician. The randomization will be stratified based on study recruitment site, concurrent use of a serotonin-norepinephrine reuptake inhibitor, and chronic low- or high-dose opioid therapy. Allocation will be conducted by the research pharmacist and will occur after consent and completion of the first visit. At all times, the allocation assignment will be concealed from the study coordinator and other investigators who manage participant recruitment and follow-up. Allocation concealment is maintained using a centralized pharmacy administration of study drug. Both study agents are designed to look identical to each other to maintain blinding.

11. Sample size

To calculate the statistical power for our analytical strategies, we simulated scenarios for which we instilled known relationships between the random effects of change models as well as a range of predictors of those parameters that were themselves correlated. A sample size of 250 was to determine to provide substantial power (> 90%) to detect clinically significant differences between a null model versus a demographic/perioperative + psychosocial predictors model using a likelihood ratio test. An example of the expected differences is displayed (left) that illustrates a three-way interaction between treatment (Placebo vs Gabapentin), cognitive-affective style (Optimist vs Catastrophizing), and pupil size (Low, Mid, High).

12. Framework

Superiority testing will be used to examine difference between the effect of treatment alone on the change process in pain after surgery and the effect of treatment as interacting with preferred cognitive style and pre-surgery pupil responses to painful stimuli.

13a. Information on interim analyses

There are no planned interim analyses.

13b. Any planned adjustment of the significance level due to interim analysis

None.

13c. *Details of guidelines for stopping a trial early*

There is no plan to stop the trial early aside from recommendations based on unanticipated serious adverse events by the DSMB.

14. *Timing of final analysis*

Table 1. Timing of study measures

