Study period	Screen	Baseline	In hospital	Daily diaries	Follow up 1	Follow up 2	Phone	Orthopaedic clinic visits
Visit number	0	Visit 1			Visit 2	Visit 3		
Week		-4 to -2*	0-3 days	0-8	8	26	12,16,20,52	2, 6, 12-16, 26, 52
Informed consent		X						
Demographic		X						
Medical/surgical history		X						
Questionnaires		X			X	X		
Pain testing & pupillometry		X						
Randomisation		X						
Study drug dispensing		X						
In hospital pain/medication data & disposition			X					
Daily diary & accelerometry		X		X				
Phone assessment of pain, medication use, function							X	
Joint function								X

*Study medication begins at -2 weeks and continues until 3 weeks after surgery

Final analysis of the gabapentin vs placebo comparison with and without inclusion of interactions with preferred cognitive style and pre-surgery pupil responses to pain will take place when all patients have completed the 12-month follow-up and data for the primary endpoint have been cleaned, which occurred in May 2022. Results were anticipated to be posted by Jan, 2023, but complexities associated with generation of a novel psychologic construct from the final dataset and defining parameters for pupil assessment prevented completion of the primary analysis until Mar, 2023.

15. *Timing of outcome assessments*

The schedule of study procedures is provided in the protocol and summarized in the table below.

Section 4: Statistical Principles

16. *Level of statistical significance*

All applicable statistical tests will be 2-sided and will be performed using a 5% significance level.

17. *Adjusting for multiplicity*

The primary analysis involves a single model-based inference that will be interpreted at the 5% threshold of statistical significance. If the primary analysis is significant, each main factor, all two way interactions, and the three way interactions will be evaluated and each will be interpreted at the 5% level of significance with no adjustments made for multiplicity.

18. *Confidence intervals*

All confidence intervals presented will be 95% and two-sided.

19a. *Definition of adherence to the intervention and how it is assessed*

Compliance is assessed based on the number of daily diary entries after hospital discharge. It is defined as:

$$\% \text{ compliance} = (\text{number of entries}/\text{number of days entries were to be completed}) * 100\%$$

19b. *How adherence will be presented*

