The primary analysis will model trajectory of recovery of daily worst pain ratings and examine several sources of influence on this recovery. Sometimes referred to as mixed-effects models, or hierarchical linear models, growth curve modeling allows specification of a change trajectory that is unique to each individual. The nature of the common form of changes in daily pain will be modeled using a curvilinear form (e.g., polynomial regression). Through the use of fixed and random effects, variations in intercepts (i.e., levels of pain on day of discharge) and slopes (i.e., change in daily pain over time) can be examined using the pre-specified influences outlined below. To model individual pain trajectories, several model form candidates will be examined with the best fit determined using a Bayesian Information Criterion. These model forms will include linear, quadratic, cubic, and log(time), and each of these model candidates will be employed that reflect a fundamental change in trajectory that occurs during the observation period. Based on preliminary data it is highly likely that a log(time) form will be chosen.^{1,2}

To examine the proposed hypotheses, several key sets of predictors will be specified including patient characteristics, operative characteristics, cognitive style, randomized treatment assignment, and pre-operative pupil diameter response. Each of these predictors are described below:

Patient characteristics: To adjust the associations for individual age and sex will be entered into the model.

Operative characteristics: To adjust the associations for any subtle differences in medical care, study site, and surgery type (hip or knee arthroplasty) will be entered into the model.

Cognitive style: Multidimensional scaling of the pre-operative questionnaires will be conducted to create a unidimensional scale that represents a broader spectrum of cognitive style that ranges from optimism/acceptance of pain to catastrophizing. This novel predictor will be examined for reliability and correlations with the original scales. If insufficient reliability ($\alpha < 0.70$) or construct validity ($r < |0.40|$) with the original scales cannot be obtained, the analysis will proceed using the originally scaled catastrophizing predictor.

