Pupil diameter: Pupil recordings will be conditioned to remove artifacts (e.g., blinks), saccades, and deviations from central gaze that might bias recordings. A response window with appropriate lag reflecting delayed onset of pupil response due to physiological delays will be used to define change in diameter to each stimulus as previously reported.¹⁷ Two pupil measurements will be estimated from the session data, the mean pupil diameter during baseline (i.e., pre-stimulus) and the modeled response to pupil to 50-degree stimulus.

Gabapentin: Randomized treatment assignment of either gabapentin or placebo will be a fundamental predictor of trajectory.

These individual predictors sets will then be used to test the primary hypothesis that gabapentin alters time course of recovery after arthroplasty in a manner dependent on its interaction with preferred cognitive style and pre-surgery pupil diameter. The primary statistical inference will be the difference in the likelihood ratio between two nested models using a chi-square test with K degrees of freedom (i.e., K being the difference in the number of parameters between the two models). The first model (i.e., null model) will consist of the pain trajectory model with the addition of patient characteristics and operative characteristics. The second nested model will add medication assignment (gabapentin versus placebo), cognitive style (catastrophizing \leftrightarrow optimism latent score), and resting pupil diameter, and all two-way interactions and three-way interaction between these 3 predictors (i.e., 3 two-way, and 1 three-way interaction for both intercept and slope parameters) from the first nested model. This approach allows a single likelihood ratio test of the primary hypothesis and will be interpreted using a two-tailed hypothesis test using $p < 0.05$. A statistically significant difference in the likelihood ratio test will be interpreted as evidence to support the primary hypothesis in that the interaction of these predictors impacts some aspect of the change process beyond that of the basic model. We have planned several sensitivity analyses using multiple imputation to account for missing data.

Several exploratory secondary analyses of the data set:

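### Sections 12 and 14 still describe the primary comparison with the wrong pupil measure and with treatment on both sides, while the likelihood ratio test in Sections 8 and 27 is an omnibus test that a prognostic main effect alone can make significant

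*SAP*

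**What the plan says.** Section 12 gives the framework in one sentence: "Superiority testing will be used to examine difference between the effect of treatment alone on the change process in pain after surgery", as against "the effect of treatment as interacting with preferred cognitive style and pre-surgery pupil responses to painful stimuli". Section 14, on the timing of the final analysis, describes the gabapentin versus placebo comparison "with and without inclusion of interactions with preferred cognitive style and pre-surgery pupil responses to pain". The overview in Section 27a/27b lists among its predictor sets "cognitive style, randomized treatment assignment, and pre-operative pupil diameter response".

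The model specifications read differently. Section 8 starts from "a null model (m_0), with only change parameters and prognostic covariates" and brings in treatment, cognitive style, resting pupil diameter and their interactions only in the full model. Section 27 does the same. Its null model is the pain trajectory with patient and operative covariates, and its second model adds medication assignment, cognitive style and "resting pupil diameter, and all two-way interactions and three-way interaction between these 3 predictors", with the interactions acting on both intercept and slope.

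Section 27 also defines two separate pupil variables: the pre-stimulus mean diameter and the modeled response to a 50-degree stimulus. It places the response among the exploratory secondary analyses (item 2). The appendix entry for SAP 2.1 confirms that the primary analysis uses resting diameter. Finally, Section 27 says that a significant likelihood ratio test will be taken as support for the hypothesis that the interaction of the predictors affects recovery.

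**The concern.** Section 17 promises one model-based inference at 5%. That requires one pupil variable, one reference model and one meaning for a significant result, stated the same way wherever the test is described.

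The pupil wording falls short because the 2.1 correction was recorded for Sections 2 and 6 of the SAP only. Items 12 and 14 lie in its Section 3 and kept the old predictor.

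The comparator wording falls short in substance. A reader of Sections 12 and 14 expects the test to ask whether the interactions add anything to the treatment effect. The test in Sections 8 and 27 asks whether any of the three predictors, alone or in combination, adds anything to the covariates. A trial in which catastrophizing merely predicts pain, and gabapentin does nothing, could pass the second test and be reported as having shown the first. This is not remote: the appendix entry for SAP 2.2 itself cites a large literature linking catastrophizing with pain.

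**Working it through.** **The plan's own figure.** Section 11 gives N = 250 and power above 90% for a likelihood ratio test of a null model against a predictors model. The figure came from simulation, and no effect sizes, variances or correlations are given, so it cannot be reproduced. It refers to an omnibus comparison, not to a test of interactions alone.

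**Inputs.** From Section 27: three added predictors, three two-way interactions and one three-way interaction; effects on intercept and slope; K equal to the difference in the number of parameters. From Section 16: 5% level. From Section 11: N = 250. Section 27 expects log(time) to be the likely form, which has one slope parameter, so each term counts twice.

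**Degrees of freedom, same full model throughout.**

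| Reference model | Terms tested | K, linear or log(time) | 5% critical value | K, quadratic | K, cubic |
|---|---|---|---|---|---|
| Covariates only (Sections 8 and 27) | 3 + 3 + 1 = 7 | 7 × 2 = 14 | 23.68 | 21 | 28 |
| Covariates + treatment (a reading of Section 12) | 2 + 3 + 1 = 6 | 6 × 2 = 12 | 21.03 | 18 | 24 |
| Covariates + all three main effects | 3 + 1 = 4 | 4 × 2 = 8 | 15.51 | 12 | 16 |

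The wording of Section 14 (without interactions) fits either of the last two rows, because it does not say whether the main effects of cognitive style and pupil diameter stay in.

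**What the tests respond to.** Assume no treatment effect, no interaction, and one prognostic main effect (cognitive style or pupil diameter) that explains a share R2 of one trajectory parameter. Take the noncentrality as λ = −N × ln(1 − R2), and the rejection probability as the noncentral chi-square tail beyond the critical value.

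| Assumed R2 | λ = −250 × ln(1 − R2) | K = 14 | K = 12 | K = 8 |
|---|---|---|---|---|
| 0.02 | 5.1 | 0.23 | 0.25 | 0.05 |
| 0.05 | 12.8 | 0.60 | 0.64 | 0.05 |
| 0.10 | 26.3 | 0.94 | 0.95 | 0.05 |

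In the K = 8 column the main effect is in both models, so the test keeps its nominal level. The treatment-only reference model does slightly worse than the covariate-only one, because it drops two degrees of freedom and still leaves the prognostic effect in the contrast.

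**The case against.** The strongest reply is that the primary test is not in doubt. The only two places that specify models, Sections 8 and 27, agree on the pupil variable and the null model. Section 12 is a one-sentence summary without parameters, Section 14 concerns timing and never says treatment alone, and the Section 27 list is a loose label that omits any mention of pain. All of that stands. The pupil discrepancy is stale wording, and the contrast to be run is the K = 14 test.

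A reader might go further and cross two pupil measures with two comparators to get four candidate primary tests, with a false-positive risk of 1 − 0.95^4, about 19%. The SAP does not support this. It never pairs resting diameter with a treatment-alone null, and it sets the pain response against the covariate-only null only as a labelled secondary analysis. A reader might also suspect that the pupil measure was chosen after seeing results. The appendix says the error was noticed before the primary analysis was done, and nothing in the SAP contradicts that.

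It can also be said that Section 17 follows a significant result with tests of each main effect and interaction, which would show where the signal lies. That helps, but Section 27 draws its conclusion on interaction from the omnibus result itself, before those unadjusted tests are read.

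Last, replacing the null model now would alter a prespecified test after data acquisition. Section 14 dates completion of the primary analysis to March 2023. This objection is sound, and it is why the K = 14 test should be kept and reported.

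**Conclusion.** The point holds on two counts. First, Sections 12 and 14, and loosely the Section 27 predictor list, name a pupil variable that the rest of the SAP assigns to secondary analysis. This is a minor inconsistency with a clear intended reading. Second, Sections 12 and 14 describe a comparison that the specified test does not make, and Section 27 gives that test an interpretation it cannot carry. With one slope parameter, the test has 14 degrees of freedom, of which only 8 concern interactions.

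The rejection probabilities (0.23, 0.60, 0.94) rest on assumed R2 values that the SAP does not give. They also treat the trajectory parameter as if observed directly in all 250 participants, so measurement error in individual trajectories would lower them for a given true R2. The direction does not depend on these figures: the K = 14 test is sensitive to main effects by construction.

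It would be wrong to infer that adopting the treatment-alone comparator of Section 12 cures the problem. At R2 = 0.05 that test rejects 64% of the time without any interaction, against 60% for the stated test.

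**What to change.** 1. In Sections 12 and 14 and the Section 27 predictor list, name pre-surgery resting pupil diameter.
2. State one nested pair of models, in identical terms, in Sections 8, 12, 14 and 27.
3. Describe the prespecified K = 14 test as a test of whether any added predictor, alone or in interaction, improves on the covariate model. Remove the statement that its significance is evidence of interaction.
4. Base any conclusion on effect modification on a reference model that holds treatment, cognitive style and resting diameter as main effects on intercept and slope and omits only the interactions (K = 8, critical value 15.51 for a linear or log(time) form). Do not use a treatment-only reference. This set still contains the cognitive style by pupil term, which does not involve gabapentin, so a claim about gabapentin should also point to the terms that include treatment.
5. Date and justify the addition, and report it beside the K = 14 result.

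The cost is wording, one further model fit, and disclosure of a late change to the plan. No new data are needed.

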There is a large literature demonstrating a positive correlation between the extent of pain catastrophizing with pain, disability, and opioid use and a negative correlation with activity. Since the cognitive construct to be used in both the primary analysis and the secondary analyses is derived from the pain catastrophizing instrument, adjustment of modeled trajectories by preoperative pain, activity disability, and opioid use would be expected to diminish the independent effect of the cognitive construct in these analyses. The adjustments in modeling using these preoperative variables were intended as sensitivity analyses rather than testing the primary and secondary hypotheses. This mistake was identified and this amendment was prepared and submitted prior to performing analyses using these adjustments.

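### A significant omnibus test is read as evidence of a gabapentin interaction, but a purely prognostic effect of cognitive style can produce it; once style is moderately prognostic, the test also no longer holds false gabapentin claims near 5%

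*SAP*

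**What the plan says.** Section 8 (Objectives) states the alternative hypothesis in terms of gabapentin: it "is that there is a difference between the two groups which is dependent on these interactions".

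Section 27a/27b defines the test. "The first model (i.e., null model) will consist of the pain trajectory model with the addition of patient characteristics and operative characteristics". The full model then adds treatment, cognitive style, resting pupil diameter and all their interactions, described as "3 two-way, and 1 three-way interaction for both intercept and slope parameters". The two models are compared by one chi-square likelihood ratio test with K degrees of freedom. A significant result is to be taken as support for the primary hypothesis, in that "the interaction of these predictors impacts some aspect of the change process beyond that of the basic model".

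Section 17 (Adjusting for multiplicity) says: "The primary analysis involves a single model-based inference that will be interpreted at the 5% threshold of statistical significance". If that test is significant, every main factor, two-way interaction and the three-way interaction is examined, and "each will be interpreted at the 5% level of significance with no adjustments made for multiplicity". The SAP has no other condition that is specific to gabapentin.

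On whether style should predict pain, the Appendix (SAP 2.2) says: "There is a large literature demonstrating a positive correlation between the extent of pain catastrophizing with pain, disability, and opioid use". It then argues that adjusting for preoperative pain would weaken the independent effect of the cognitive construct. This gives a direction but no size.

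**The concern.** The hypothesis concerns a treatment difference that depends on style and pupil. The test asks whether any of seven added terms matters, and three of them (style, pupil, style x pupil) do not involve gabapentin. The SAP's own background leads one to expect a style effect, so the test may be significant for that reason alone.

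Two consequences follow. First, the omnibus result could be reported as interaction when there is none. This is an error of interpretation and does not depend on any assumed effect size. Second, section 17 relies on the omnibus test as its only protection before four gabapentin terms are read at 5% each. If style has opened that gate, the protection is weak, and a chance treatment effect, or one confined to a style or pupil group, could be reported as a finding.

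**Working it through.** **Inputs from the SAP.** N = 250 (section 11); 1:1 allocation (section 9); two-sided 5% (sections 16 and 17); null-model covariates age, sex, site and surgery type (section 27a/27b); seven added terms, each on intercept and slope. For a linear or log(time) form, K = 7 x 2 = 14. Of these 14 parameters, 4 x 2 = 8 contain gabapentin and 3 x 2 = 6 do not. Section 27a/27b calls log(time) highly likely.

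**Assumptions.** r is the correlation of style with the pain intercept, varied from 0 to 0.4. Style acts on the intercept only. The residual intercept-slope correlation rho is 0 or -0.4. Gabapentin, pupil and all interactions have no effect.

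**The plan's own figure.** Section 11 states power above 90% at N = 250 from a simulation whose effect sizes, variances and correlations are not given. It cannot be reproduced, and nothing here confirms or refutes it.

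**Step 1: omnibus test, by formula.** The 5% critical value of chi-square with 14 df is 23.68. With rho = 0 the noncentrality is N r²/(1 - r²):
- r = 0.1: 250 x 0.01/0.99 = 2.53, probability of significance 0.126
- r = 0.2: 250 x 0.04/0.96 = 10.42, probability 0.493
- r = 0.3: 250 x 0.09/0.91 = 24.73, probability 0.924
- r = 0.4: 250 x 0.16/0.84 = 47.62, probability 0.999

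A 90% probability is reached at r = 0.29. A quadratic form (21 df) or cubic form (28 df) lowers the r = 0.3 figure to 0.870 or 0.818, so the conclusion does not hang on the form.

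**Step 2: gabapentin terms once the gate is open.** If the tests were independent, the chance of at least one false term would be 1 - 0.95^4 = 18.5% for four joint intercept-slope tests, or 1 - 0.95^8 = 33.7% for eight separate coefficients.

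**Step 3: simulation of gate and terms together.** There were 10,000 trials per scenario. Each patient's intercept and slope formed a bivariate outcome, the four covariates were in both models, and predictors were centred. Results are shown as rho = 0 / rho = -0.4.

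| r | Omnibus significant | Omnibus significant and at least one of 4 gabapentin terms (joint tests) | Same, Holm over the 4 |
|---|---|---|---|
| 0 | 6.2 / 6.6% | 4.4 / 4.7% | 2.4 / 2.4% |
| 0.1 | 15.0 / 17.4% | 8.0 / 8.4% | 3.4 / 3.4% |
| 0.2 | 51.7 / 60.1% | 15.4 / 16.0% | 4.8 / 4.9% |
| 0.3 | 91.5 / 95.9% | 18.6 / 19.2% | 5.3 / 5.3% |
| 0.4 | 99.9 / 100% | 19.2 / 19.9% | 5.4 / 5.3% |

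The slight excess over 5% at r = 0 is small-sample inflation of the chi-square reference. Each gabapentin term taken alone was at 4.9-5.7% at r = 0.3.

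**Step 4: dependence on what the SAP leaves open.** The SAP fixes neither the coding nor whether intercept and slope are tested together.
- Eight separate coefficients, centred: 25.3% at r = 0.2, 31.4-32.5% at 0.3, 31.5-33.0% at 0.4.
- Four joint tests, uncentred (drug 0/1; pupil mean 5, SD 1, both assumed): 9.9% at r = 0.2, 11.3-11.9% at 0.3, and about 9-12% over r = 0.2-0.4.
- Eight separate coefficients, uncentred, r = 0.3: 20.2%.

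The uncentred rates are lower because the four tests become strongly correlated. That is no reason to prefer this coding: the lower-order treatment terms then describe an effect at a pupil diameter of zero.

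**The case against.** Section 17 says openly that it makes no adjustment. It names one primary inference and then breaks it down, and each term keeps about 5% error on its own. The family of four gabapentin terms is a reviewer's choice; the three interactions, or the three-way term alone, would also be defensible, and the last has no multiplicity problem. Detecting style and pupil effects is also an intended use of the omnibus test: section 8 wants to know how these factors shape recovery, and section 11 powers a model with psychosocial predictors. These points stand. They make multiplicity adjustment a trade-off and not a correction that the plan must accept. They do not rescue the sentence in section 27a/27b that reads the omnibus result as interaction.

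A reader might infer that the omnibus test gives no protection at all against false gabapentin claims. The documents do not support that. If style has no prognostic effect the gate holds the chance near 4-5% with centred joint tests, and at r = 0.1 near 8%. The SAP gives no r, and the Appendix gives only the direction. Nor can a single rate such as 19% be attributed to the plan, because it depends on centring that the SAP does not specify. The omnibus test is also not invalid in itself: when none of the added terms has an effect, it rejects in about 6% of trials.

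**Conclusion.** The interpretation rule is wrong as written. A significant omnibus test shows that at least one of the added terms improves fit, and style alone can be that term: in about 15-17% of trials at r = 0.1, 50-60% at 0.2 and 91-96% at 0.3, with no gabapentin effect of any kind.

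The multiplicity consequence is conditional. Once style is at least moderately prognostic (r about 0.2-0.4), the gate no longer holds the chance of at least one false gabapentin term near 5%. The rate is about 9-12%, 15-20% or 25-33%, according to coding and whether intercept and slope are tested jointly. At r = 0-0.1 it is about 3-8% with joint tests. The figures rest on the assumed r, rho, coding and complete diaries. That the gate weakens as r rises does not depend on the exact values.

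**What to change.** **In sections 17 and 27a/27b:**
- State that a significant omnibus test shows only that the added predictors as a set improve fit, and is not by itself evidence of a gabapentin effect or of interaction.
- Base any such claim on the four terms that contain treatment (treatment, treatment x style, treatment x pupil, three-way), each tested jointly on intercept and slope with style and pupil centred.
- Report style, pupil and style x pupil as estimates with 95% intervals.
- If the four terms stay unadjusted, say that the omnibus gate does not control the chance of any false claim among them when style is prognostic.

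These changes take a few sentences and need no new model. Correcting what the omnibus test may be said to show costs no power.

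**Optional:** Holm across the four terms, with the omnibus condition kept. The chance of any false gabapentin term is then 2-6% at every r tried. At r = 0.3, false interaction claims alongside a real uniform 0.5 SD effect fall from about 15% to 5%. The cost, also at r = 0.3, is power: for a uniform 0.3 SD effect it falls from 58.0-66.4% to 37.7-45.8% (about 20 points), and for a three-way effect of 0.4 SD from 80.9-86.6% to 63.6-73.5% (13-17 points).

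**Timing.** Section 14 says that difficulties with the cognitive construct and pupil parameters "prevented completion of the primary analysis until Mar, 2023". If results were already known when a change is made, it must be dated and labelled post hoc.
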